• Exclusion of subjects with untreated systemic helminth infestations or subjects who have failed to respond to standard of care therapy; neutralisation of IL-13 might theoretically cause a worsening of parasitic infestation, in particular prevention of expulsion of gastrointestinal worms (helminths) (Bancroft et al. 2000).

- Exclusion of subjects with a history of tuberculosis requiring treatment within 12 months prior to the screening visit.
- Exclusion of subjects with a history of a clinically significant infection (defined as a systemic or serious skin infection requiring parenteral antibiotics, antiviral, or anti-fungal medication; see Section 8.3) within 4 weeks prior to baseline which, in the opinion of the investigator or sponsor's medical expert, may compromise the safety of the subject in the trial.

In conclusion, previous clinical experience with tralokinumab shows no major safety or tolerability concerns, and appropriate measures have been instituted in this trial to protect subjects from potential risks that have been previously identified and to sufficiently monitor each subject. The current risk/benefit profile is considered favourable and supports the administration of tralokinumab with or without TCS therapy for the purposes of achieving the objectives of this trial.

The current COVID-19 pandemic may warrant many subjects in the ECZTEND trial to stay at home to comply with authority-issued preventive measures, which may impact subjects' ability to attend visits at the trial site. To follow authorities' restrictions and to safeguard the subjects in the ECZTEND trial as well as providing continued therapy to secure the scientific integrity, the clinical trial protocol provides an opportunity for telephone visits and courier delivery of IMP and pregnancy tests to subjects in replacement of the site visits (see Appendix 3K for details).

Page 47 of 187

6 Trial objectives and endpoints

Panel 6: Objectives and endpoints

Objectives	Endpoints
Primary objective	Primary endpoint
To evaluate the long-term safety of tralokinumab	Number of adverse events during the treatment period from baseline up to Week 268
Secondary objectives	Secondary endpoints

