14.3.8.1 Adverse events

AEs will be coded during the course of the trial according to Medical Dictionary for Regulatory Activities (MedDRA). AEs will be presented by preferred term and primary

Version: 14.0 Page 108 of 187

system organ class (SOC) as percentage of subjects with AEs, number of AEs, and rate of AEs (number of AEs per 100 patient-years of exposure).

Only treatment-emergent AEs will be summarised; however, all AEs recorded during the course of the trial will be included in subject data listings. An AE will be considered treatment-emergent if started after the first use of IMP, or if started before the first use of IMP and worsened in severity after first dose of IMP. The tabulations described in the following will only include treatment-emergent AEs. In each of the tabulations, AEs are defined by MedDRA preferred term within primary SOC.

An overall summary of the number of AEs, the rate of AEs (number of AEs per 100 patient-years of exposure), the number (percentage) of subjects with any treatment-emergent AEs, deaths, SAEs, withdrawals from the trial due to AEs, treatment-related AEs, and severe AEs will be presented. The above summaries will also be made separately for subjects who transferred from the parent trial LP0162-1334. As the frequency of site visits is reduced after May 2021, an additional overall AE summary table will be presented that excludes events and exposure time after May 2021. In addition to the overall summary, the data will be presented by tralokinumab-naïve/re-treated/continuously treated subjects.

The number of AEs, rate of AEs, and number of subjects with each type of AE will be tabulated for the total cohort of subjects and by tralokinumab-naïve/re-treated/continuously treated subjects.

The severity and causal relationship to IMP for each type of AE will be tabulated.

Related AEs are defined as AEs for which the investigator has not described the causal relationship to IMP as 'not related'. The number of subjects with each type of related AE will be tabulated.

SAEs and AESIs will be evaluated separately. A narrative for each SAE will be given. AESIs and AEs leading to withdrawal from the trial will be tabulated and listed.

AEs leading to withdrawal from trial will be listed.

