5.4.3 Extent of exposure and treatment compliance

Exposure

Exposure to treatment will be presented for the SAF as days of exposure in total, by exposure time cutoffs, and by parent trial.

Days of exposure will be calculated as the number of days from the date of the first IMP dose in ECZTEND to the date of the end of treatment visit, or – if the end of treatment visit is missing – to the date of permanent discontinuation of IMP.

Treatment compliance

Adherence will be presented for the SAF.

The above will also be made for subjects transferring in from LP0162-1334. However, only presenting summaries of the total, tralokinumab naïve, re-treated, and continuously treated, not the washed-out subjects.

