5.5 Primary analysis

The primary endpoint in this trial is the number of adverse events during the treatment period from baseline up to Week 268, and the analysis of this endpoint is covered in the safety analysis section.

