5.6.2.2.3 Supplemental analyses

A supplementary analysis will be appended for the primary analysis, where each estimated percentage of days in response will be used to analyse the endpoint rephrased in to "subjects with $\geq x\%$ of days in response" where x is defined as the whole numbers 0, 1, 2, ...,100. The subsequent proportion of subjects with $\geq x\%$ of days in response will be estimated with 95% Wilson CIs.

The second supplementary analysis, will be re-made for the primary and the above supplemental analysis over the following periods: Week 0-<16, Week 16-<104, Week 104-<200, and Week 200-264, in addition to the overall treatment period.

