5.8.1 Adverse events

AEs will be coded during the course of the trial according to MedDRA version 20.0 but analysed in MedDRA version 27.0.

Only TEAEs will be summarized in this trial. AEs were considered treatment emergent if they started after first dose of IMP or started before first dose of IMP and worsened in severity after first dose of IMP. All AEs recorded during the trial will be listed.

For the treatment and SFU periods, presentations of AEs by SOC and PT will include summaries of the following categories of AEs:

- All AEs.
- Frequent AEs (\geq 5% of subjects reporting the AE in the total population).
- Frequent AEs (occurring with an incidence rate ≥ 2.5 in the total population).
- SAEs.
- AEs leading to withdrawal from the trial.
- Probably or possibly related AEs.
- Severity of AEs (mild, moderate, and severe AEs presented separately).

Summaries will include the percentage and number of subjects with an AE, number of AEs, patient-years of exposure up until the first event, incidence rate of AEs (rate of new events/occurrences, calculated as the number of subjects with an AE per 100 patient-years of exposure at risk defined as patient-years up until the first event or end of exposure [whichever came first]), and occurrence rate of AEs (rate of events/occurrences calculated as the number of AEs per 100 patient-years of exposure up until end of exposure).

Overviews of AEs will be appended for the above-mentioned categories of AEs and will include the following information: SAEs, severity (mild, moderate, or severe), relationship to IMP (probably, possibly, and not related), AEs probably or possibly related to IMP, AEs leading to withdrawal from trial and/or permanent discontinuation of IMP, outcome, and action taken with IMP.

For the SFU period, all AEs and SAEs will be presented by an overview summary and by SOC and PT using the safety follow-up analysis set.

The above summaries will also be made separately for subjects who transferred from the parent trial LP0162-1334. Secondly, as the frequency of site visits is reduced after May 2021, 2 additional overall AE summary tables will be presented, one will exclude events and exposure time after May 2021 and the second will only include events and exposure time after May 2021. Thirdly, the data will be presented by tralokinumab naïve, re-treated, and continuously treated, and by washed-out subjects using the above defined summaries.

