5.8.1.1 ECZTEND defined adverse events of special interest (ECZTEND-AESI)

ECZTEND-AESIs will be presented overall within each AESI, and by SOC and PT, as defined for TEAEs. Additionally collected information for each of the defined ECZTEND-AESIs will be summarised. For their definition see Panel 6.

AESIs	Reason for inclusion
	Eczema herpeticum is a well-known severe skin infection in patients with AD.
Eczema herpeticum	Eczema herpeticum occurs in lesioned AD skin – the additional information collected can be used to adjudicate the events, if needed.
Malignancy diagnosed after treatment assignment, excluding basal cell carcinoma, localised squamous cell carcinoma of the skin, and carcinoma in situ of the cervix	There has been no indication of a higher risk of malignancy with tralokinumab treatment compared with placebo. However, as is typical for immunomodulating biologics, malignancy is considered an important potential risk for tralokinumab.
Skin infections requiring systemic treatment	The skin barrier is expected to improve during treatment with tralokinumab. Additional information is collected to better describe location and pathogen.
Conjunctivitis**	Important potential risk in the tralokinumab risk management plan. Due to focus on eye disorders.
Keratoconjunctivitis**	Due to focus on eye disorders.
Keratitis**	Due to focus on eye disorders.

Panel 3: AESIs (as defined in the CTP)

**: grouped in AESI 'Eye disorders'

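### AE, SAE, AESI and ADR rates are pooled over up to 268 weeks, with none by time since first ECZTEND dose, so a late rise in risk would be diluted

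*SAP*

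**What the plan says.** Protocol section 6 (Panel 6) gives the primary objective: "To evaluate the long-term safety of tralokinumab". SAP 5.5 gives the primary endpoint as the "number of adverse events during the treatment period from baseline up to Week 268" and refers its analysis to the safety section.

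SAP 5.8.1 defines two rates for the treatment period. The occurrence rate is the "number of AEs per 100 patient-years of exposure up until end of exposure". The incidence rate counts subjects with an event and stops exposure at the first one. SAEs are one of the tabulated categories. For the AESIs, SAP 5.8.1.1 says "ECZTEND-AESIs will be presented overall within each AESI, and by SOC and PT, as defined for TEAEs", and 5.8.1.2 treats ADRs the same way. None of these is divided by time on treatment.

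The time split that does exist is by calendar date. Because site visits became less frequent, SAP 5.8.1 adds two overall AE summaries: "one will exclude events and exposure time after May 2021 and the second will only include events and exposure time after May 2021". Protocol 14.3.8.1 plans only the first: "an additional overall AE summary table will be presented that excludes events and exposure time after May 2021".

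Other data are resolved by time on treatment:
- Exposure is shown as "days of exposure in total, by exposure time cutoffs, and by parent trial" (SAP 5.4.3); protocol 14.3.3 uses yearly periods.
- Proportion of time in response is repeated over "Week 0-<16, Week 16-<104, Week 104-<200, and Week 200-264, in addition to the overall treatment period" (SAP 5.6.2.2.3).
- Subjects still ongoing are described at Weeks 56, 104, 152, 216 and 264 (SAP 5.3.1).
- Reasons for withdrawal and for stopping IMP are shown as Aalen-Johansen cumulative incidence (SAP 5.4.1).

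**The concern.** Protocol section 12 says the design was modified to obtain safety data for up to 5 years, and section 7.3 relies on that duration as suitable for judging long-term safety. No planned rate isolates the later years. A pooled occurrence rate is dominated by the first years, when most subjects are on treatment. For common events the incidence rate leans further towards early treatment, because each subject leaves the denominator at the first event.

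What is at stake is whether the report can say anything direct about risk in years 4 and 5, and how much exposure such a statement rests on. SAP Panel 3 lists malignancy as a potential risk that needs attention, and malignancy has no planned time split.

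**Working it through.** **No figure to reproduce.** The plan states about 1,600 subjects, no formal sample size (protocol 14.1) and no testing (SAP section 2). The check is of what the planned tables can show.

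**1. What the May 2021 tables separate.** The protocol synopsis gives a maximum of 140 weeks of treatment for subjects stopping at end of May 2021. Counting back 140 weeks from 31 May 2021 gives an earliest baseline of about 24 September 2018; no first-dose date is stated. So:
- all exposure beyond Week 140 lies in the later table;
- no subject is past Week 140 at the cut, so anyone treated past Week 156 first adds at least 156 - 140 = 16 weeks of earlier treatment time to that table, and later entrants add more. Amendment 7 admitted LP0162-1343 and TRA-WEI-0015-I subjects, who start late;
- the later table coincides with the reduced-visit schedule.

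It is therefore a partial early/late contrast, not a split by duration.

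**2. Dilution formula.** If the rate is multiplied by k after some time, and a share s of all patient-years falls after that time, then

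pooled rate ratio = (1 - s) + k x s = 1 + (k - 1) x s.

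**3. The share s.** It depends on entry dates, retention and country closure, which the documents do not give. Two illustrations follow, neither of them a bound.

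*With country closures.* Country end dates are taken from protocol Panel 17, which labels them estimates. From 24 September 2018 to end of August 2021 is 1,072 days, so treatment in Germany is at most about 153 weeks. Subjects from LP0162-1334 have a stated maximum of 114 weeks. On those dates, neither group contributes after Week 156. The assumptions were:
- three country mixes;
- adult entry spread uniformly over 1.0 to 2.6 years;
- re-consent of 50-90%;
- withdrawal of 8-25% per year;
- an adolescent share of 0 or 8%;
- a late-entry share of 0 or 10%.

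Across the 432 combinations, s after Week 156 runs from 2.7% to 17.2%. For k = 2 the pooled ratio is 1 + 0.027 = 1.03 to 1 + 0.172 = 1.17.

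*Without country closures.* Assume exponential loss at h per year and a maximum of T = 268 x 7/365.25 = 5.14 years. The share after year 3 is (e^(-3h) - e^(-Th)) / (1 - e^(-Th)).
- h = 0.2: (0.549 - 0.358)/(1 - 0.358) = 0.297, ratio 1.30.
- h = 0.7: (0.122 - 0.027)/(1 - 0.027) = 0.098, ratio 1.10.

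**4. The same doubling in the May 2021 pair.** With uniform entry over the 140 weeks before the cut, no closures and h of 0.2 to 0.5, the share of the later table beyond year 3 is 27% to 18%. A doubling then shows as 1.27 to 1.18 in the later table and 1.00 in the earlier one. The pair shows part of a rise, for overall AE and SAE summaries only.

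**5. Precision of a late band.** The median exposure after Week 156 over the 432 combinations is 231 patient-years. At an assumed 1 per 100 patient-years that is about 2 events. The exact Poisson limits for 2 events are 0.242 and 7.225. Divided by 231 and multiplied by 100, they give 0.1 to 3.1 per 100 patient-years, an interval that contains both the assumed rate and twice that rate.

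**The case against.** Four points can be made for the plan as written.

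- **Some safety information is already resolved in time.** The SAP 5.4.1 curves show withdrawal and IMP discontinuation over the treatment period, and protocol 10.2.2 lists adverse event among the recorded reasons. The same section makes malignancy, with the exclusions used in the AESI definition, a ground for withdrawal, so such cases should enter the curve when recorded under that reason. This stands as a qualification. However, the curve pools all AE withdrawals, omits AEs that do not end participation, and gives no AE, SAE or AESI rate.
- **The May 2021 pair carries SAEs.** This also stands. The overall summaries include SAEs, and the earlier table holds only exposure up to Week 140. The remaining gap is duration bands, and any time split at AESI or SOC/PT level.
- **Nothing promised is missing.** The endpoint is a count to Week 268 in a single-arm trial without testing, and the planned tables deliver it. All AEs are listed, so banding could be done later. True, but listings give no denominators, and bands fixed in the plan are more credible than bands chosen after seeing the events.
- **Late bands would be imprecise and confounded.** Correct, and it limits what the added tables can claim. The pooled rate mixes in the same selected late exposure without showing how little of it there is.

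A reader might infer that the plan has no time-related safety output at all, that it contradicts its own endpoint, or that a real late signal would go unseen. The documents support none of these. The two outputs above exist, the endpoint is reported as defined, and individual late events appear in listings and SAE narratives. Nor do the documents suggest that risk actually rises late.

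**Conclusion.** The point holds in a limited form: no AE, SAE, AESI or ADR rate is planned by time since first ECZTEND dose, and two planned outputs cover the gap only in part. The direction of the dilution follows from the rate definition. Its size rests on assumptions: a doubling after Week 156 shows as about 1.03-1.17 in the pooled rate if 3-17% of exposure falls there, and as 1.10-1.30 if closures are ignored and 10-30% falls after year 3. No planned result is invalidated. The change is worth making because the primary objective concerns long-term use and the data needed are already collected. It would not turn the trial into one that can detect or exclude a late doubling of a rare event.

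**What to change.** In SAP 5.8.1 and 5.8.1.1, add descriptive tables for all AEs, SAEs and each of the six AESIs by time since first ECZTEND dose.

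- **Intervals:** one set throughout, Weeks 0-<52, 52-<104, 104-<156, and 156 to end of treatment. The response windows in SAP 5.6.2.2.3 do not serve, since they have no break at Week 156 and end at Week 264.
- **Content:** event counts, patient-years, subjects at risk and occurrence rates with 95% CIs. For all AEs, use a variance that allows for repeat events within a subject.
- **Groups:** overall and, for all AEs and SAEs, by naive, re-treated and continuously treated group. TRA-WEI-0015-I subjects appear only in the overall table, because SAP 7.1 leaves them unclassified.
- **Reading:** place the tables beside the ongoing-subject tables (SAP 5.3.1) and the withdrawal curves (SAP 5.4.1). State that exposure after Week 156 comes only from subjects who consented to continue, on the reduced site-visit schedule, in countries still open; that there is no control arm; and that parent-trial exposure is not added.
- **Keep** the two May 2021 tables.

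The cost is 8 categories x 4 intervals = 32 rate cells overall, plus 2 categories x 4 intervals x 3 groups = 24, so 56 in all. No new data are needed. The downside is wide late intervals (for example 0.1-3.1 per 100 patient-years for 2 events in 231), and a late trend that cannot be separated from re-consent, fewer site visits, country closure and selective dropout.

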5.8.1.1 ECZTEND defined adverse events of special interest (ECZTEND-AESI)

ECZTEND-AESIs will be presented overall within each AESI, and by SOC and PT, as defined for TEAEs. Additionally collected information for each of the defined ECZTEND-AESIs will be summarised. For their definition see Panel 6.

AESIs	Reason for inclusion
	Eczema herpeticum is a well-known severe skin infection in patients with AD.
Eczema herpeticum	Eczema herpeticum occurs in lesioned AD skin – the additional information collected can be used to adjudicate the events, if needed.
Malignancy diagnosed after treatment assignment, excluding basal cell carcinoma, localised squamous cell carcinoma of the skin, and carcinoma in situ of the cervix	There has been no indication of a higher risk of malignancy with tralokinumab treatment compared with placebo. However, as is typical for immunomodulating biologics, malignancy is considered an important potential risk for tralokinumab.
Skin infections requiring systemic treatment	The skin barrier is expected to improve during treatment with tralokinumab. Additional information is collected to better describe location and pathogen.
Conjunctivitis**	Important potential risk in the tralokinumab risk management plan. Due to focus on eye disorders.
Keratoconjunctivitis**	Due to focus on eye disorders.
Keratitis**	Due to focus on eye disorders.

Panel 3: AESIs (as defined in the CTP)

**: grouped in AESI 'Eye disorders'

5.8.1.2 Adverse drug reactions

These ADRs of tralokinumab (as of writing this SAP) will be presented in the same way as for the AESIs. The ADRs of tralokinumab are defined in Panel 7.

5.8.2 Vital signs

Vital signs will be tabulated as described in the CTP Section 14.3.8.2. However, only presenting summaries of the total, tralokinumab naïve, re-treated, and continuously treated, not the washed-out subjects.

Additionally, vital sign values will be considered potentially clinically significant if satisfying the PCS criteria specified in the ADRG. All post-baseline measurements (including samples from unscheduled visits) will be included in the search for PCS values. Number and percentage of subjects with at least one post-baseline PCS value will be summarised with the denominator being all subjects with at least one post-baseline assessment. All PCS values will be included in the listings.

5.8.3 Physical examination

Physical examinations reported as 'abnormal, clinical significant' will be listed.

5.8.4 Clinical laboratory evaluation

Clinical laboratory evaluations will be tabulated as described in the CTP Section 14.3.8.3. However, only presenting summaries of the total, tralokinumab naïve, re-treated, and continuously treated, not the washed-out subjects.

Additionally, shift tables will be produced for relevant laboratory tests showing categories at baseline against highest or lowest test measurement in the treatment period (see Panel 4).

Panel 4: Clinical laboratory test where shift tables will be prepared for lowest/highest	
measurement in the treatment period	

Clinical laboratory test	Shift table to lowest	Shift table to highest		
Chemistry				
Sodium	Yes	Yes		
Potassium	Yes	Yes		
Creatinine	-	Yes		
Calcium	Yes	Yes		
Alkaline phosphatase	-	Yes		
Aspartate aminotransferase	-	Yes		
Alanine aminotransferase	-	Yes		
Bilirubin	-	Yes		
Cholesterol	-	Yes		
LDL cholesterol	-	Yes		
HDL cholesterol	Yes	Yes		

Clinical laboratory test	Shift table to lowest	Shift table to highest
Triglycerides	-	Yes
Glucose (non-fasting)	Yes	Yes
Hematology		
Hemoglobin	Yes	Yes
Neutrophils, segmented	Yes	-
Lymphocytes	Yes	Yes
Monocytes	Yes	Yes
Eosinophils	-	Yes
Basophils	-	Yes
Platelets	Yes	Yes

Abbreviations: HDL = high density lipoprotein; LDL = low density lipoprotein; - = not applicable.

Laboratory values will be considered potentially clinically significant if satisfying the PCS criteria specified in the ADRG. All post-baseline measurements (including samples from unscheduled visits) will be included in the search for PCS values. For haematology and chemistry laboratory parameters, the number and percentage of subjects with at least one post-baseline PCS value will be summarised with the denominator being all subjects with at least one post-baseline assessment. All PCS values will be included in the listings.

Subjects fulfilling Hy's law will be presented.

